adverse event with an increase in either arm of $\geq 5\%$ (Any Grade)	(SOC per MedDRA standard, PT within SOC by decreasing frequency for Any Grades)	Any Grades, Grade 3-4, Grade 4, Grade 5
All	PT (descending frequency of between-arm difference for Any Grades)	Worst severity: Any Grades, Grade 3-4, Grade 4, Grade 5
All	PT (descending frequency of between-arm difference for Grade 3-4)	Worst severity: Any Grades, Grade 3-4, Grade 4, Grade 5

The following data listings will also be provided with indicators for grade, relationship, seriousness, dose day of the event start/stop, days since last dose, action taken with study treatment:

- All AEs
- Grade 5 AEs
- Serious AEs other than death

8.2 Events to Monitor

The sponsor has defined a set of events to monitor (ETM) to track adverse events known to be associated with TKIs or VEGF pathway inhibition that have potentially serious consequences, or were determined to warrant ongoing routine surveillance. Each ETM is a grouped clinical term comprising a broad set of AEs that are related pathophysiologically and provide a consistent, reproducible, and transparent compilation of safety information over time. These ETMs may also be identified in the current cabozantinib product labeling (MTC US package insert and EU SmPC) or in the EU RMP document as known or potential risks and precautions.

For this study, ETMs under surveillance at the time of database lock will be considered for comparison of incidence and severity in the two treatment arms. The following summaries will be provided for ETMs:

Table 5: ETM Summaries

TEAE included	Row-levels (sorted by)	Columns		
Subject Incidence by SOC, Preferred Term and Severity				
All ETM AEs	ETM and PT	Worst severity:		
	(ETM, PT within ETM by descending frequency)	All Grades, Grade 3-4, Grade 4, Grade 5		
All ETMs of Grade >=3	ETM and PT	Worst severity:		
	(ETM, PT within ETM by descending frequency)	Grade >=3, Grade 3, Grade 4, Grade 5		
Subject Incidence by Special Criteria				
All ETM AEs by age category 3 and	ETM and PT	Worst severity:		
4, ecog, gender, prior systemic	(ETM, PT within ETM by descending frequency)	Any Grades, Grade 3-4, Grade 4, Grade 5		
anticancer therapies for MTC, race,				
region, weight				
Time to First Occurrence				
All ETM AEs and Grade >=3	Time to first occurrence of Adverse Events to			
	Monitor by Group Term			

8.3 Adverse Events of Interest

In addition, to the ETMs the following adverse events of interest (AESI) will be considered for comparison of incidence and severity in the two treatment arms:

- (i) Diarrhea
- (ii) Fistulas (includes gastrointestinal and non-gastrointestinal)
- (iii) Hemorrhage
- (iv) Hypertension
- (v) Palmar-Plantar Erythrodysesthia (PPE) syndrome
- (vi) Perforations (includes gastrointestinal and non-gastrointestinal)
- (vii) Stomatitis (includes oral mucositis/stomatitis)

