## **Safety Analysis:**

Adverse event terms will be standardized using the Medical Dictionary for Regulatory Activities (MedDRA) and tabulated by system organ class and preferred term.

Tabulations comparing the incidence and severity of the following AEs will also be provided: hemorrhage, gastrointestinal and non-gastrointestinal fistulas and gastrointestinal perforations, hypertension, diarrhea, oral mucositis/stomatitits, and PPE syndrome.

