#### 9.4.1 Adverse Events

Adverse event terms recorded on the CRFs will be mapped to preferred terms using the MedDRA dictionary. The investigator will classify the severity of AEs using the CTCAE v.4.0 and will judge each event to be "not related" or "related" to study treatment.

A treatment emergent adverse event (TEAE) is defined as any event that begins or worsens on or after the date of the first dose of study treatment.in general, only TEAEs with an onset date prior to the date of the decision for treatment discontinuation + 30 days will be tabulated in summary tables.

The frequency and percentage of subjects with TEAEs will be tabulated for overall incidence by system organ class and preferred term by treatment arm. Related TEAEs, serious TEAEs, related serious TEAEs, TEAEs resulting in study treatment discontinuation and TEAEs resulting in study treatment modification (either dose reduction or dose delay) will be similarly tabulated. TEAEs and related TEAEs will also be summarized for worst reported severity within each subject. In addition, for TEAEs of hemorrhage, GI and non-GI perforations and fistulas, hypertension, diarrhea, oral mucositis/stomatitis, and palmar-plantar erythrodysesthesia (PPE) syndrome, separate summaries will be presented. Non-GI perforations will be included in the grouped terms of non-GI fistulas. Further details of these summaries will be outlined in the SAP.

At each level of summarization, a subject will be counted only once for each AE preferred term he/she experiences within that level (ie, multiple episodes of events with the same preferred terms will be counted only once).

All reported subject deaths will be summarized by treatment arm, cause of death, and relationship to study treatment.

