2.2.3 Additional Endpoints

The following endpoints for the study will be analyzed:

- a) Safety and tolerability of cabozantinib as assessed by AEs including hemorrhage, gastrointestinal and non-gastrointestinal fistulas, gastrointestinal perforation, hypertension, diarrhea, oral mucositis/stomatitis, PPE, changes in laboratory parameters, and frequency of dose modifications
- b) Pharmacokinetics (PK) of cabozantinib
- c) Biochemical response to cabozantinib as assessed by the plasma tumor markers including calcitonin (CTN) and carcinoembryonic antigen (CEA)
- d) Pharmacodynamic effects of cabozantinib on plasma biomarkers of cabozantinib target pathway inhibition and bone turnover (will not be analyzed for the CSR)
- e) Correlation of germline and somatic genetic alterations to tumor response or resistance, cabozantinib exposure, and/or toxicity (only the effect of RET M918T subgroup on efficacy will be analyzed for the CSR)

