2.4 Study Design

This is a multicenter, randomized, double-blind, non-inferiority trial of cabozantinib at 60 mg tablet versus 140 mg capsule once daily (qd) in progressive, metastatic medullary thyroid carcinoma (MTC) subjects. Progression-free survival (PFS) evaluated by an independent radiology review committee (IRC) is the primary efficacy endpoint, with objective response rate (ORR) evaluated by the IRC as a secondary endpoint. Comparison of safety of the two dose levels are additional endpoints. For adverse events (AEs), specific events including hemorrhage, gastrointestinal and non-gastrointestinal fistulas, gastrointestinal perforations, hypertension, diarrhea, oral mucositis/stomatitis, and palmar-plantar erythrodysesthesia [PPE] will be compared between the two dose levels. The study will enroll approximately 188 subjects (94 per arm) in a 1:1 ratio to receive cabozantinib at 60 or 140 mg once daily (qd). The sample size may be increased up to 250 subjects if a review of the accumulating PFS events suggests that the 150 events required for the event-driven primary analysis will not be reached (due to censoring) among the approximately 188 subjects originally enrolled.

The study will include the following periods:

Pre-Treatment Period: Potential subjects will be screened to determine if they meet the required eligibility criteria. Screening assessments must be performed within 28 days before randomization unless otherwise specified. Qualifying images for documentation of Progressive Disease (PD) at study entry may be acquired within 4 months of randomization.

Treatment Period: Subjects who meet all eligibility criteria will be randomized in a 1:1 ratio to receive once daily either cabozantinib at 60 mg or 140 mg and matched placebo capsules and

tablets. Subjects will undergo safety and efficacy evaluations.

Tumor assessment will be performed as described in Section 2.6.

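### SAP 8.3 counts non-GI perforations with perforations, Protocol 9.4.1 counts them with non-GI fistulas, and the GI perforation comparison both documents name is given no line of its own

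*SAP*

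**What the plan says.** **Endpoint wording.** The safety and tolerability endpoint in SAP 2.2.3(a), worded as in Protocol 2.1, lists "gastrointestinal and non-gastrointestinal fistulas, gastrointestinal perforation, hypertension" among its components. SAP 2.4 repeats the list as events to be compared between the dose levels: "gastrointestinal and non-gastrointestinal fistulas, gastrointestinal perforations, hypertension, diarrhea, oral mucositis/stomatitis". The synopsis safety analysis also tabulates "hemorrhage, gastrointestinal and non-gastrointestinal fistulas and gastrointestinal perforations, hypertension". None of these lists contains a non-GI perforation category.

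**Protocol grouping rule.** Protocol 9.4.1 asks for separate summaries "for TEAEs of hemorrhage, GI and non-GI perforations and fistulas, hypertension, diarrhea, oral mucositis/stomatitis" and PPE. It then says where one of these belongs: "Non-GI perforations will be included in the grouped terms of non-GI fistulas". Further detail is left to the SAP.

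**SAP grouping.** SAP 8.3 lists seven adverse events of interest that "will be considered for comparison of incidence and severity in the two treatment arms". Item (ii) is "Fistulas (includes gastrointestinal and non-gastrointestinal" and item (vi) is "Perforations (includes gastrointestinal and non-gastrointestinal". The protocol's rule is not carried over.

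**Change control.** SAP 4.8 says substantive changes from the protocol's analyses will be fully documented in a revised plan. The V2.0 entry in the SAP version history mentions refined AE summaries in Table 4 and nothing about this grouping.

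**The concern.** A non-GI perforation belongs to the non-GI fistula group under the protocol and to the Perforations group under SAP 8.3. A programmer following one document will not reproduce the counts of a programmer following the other. The SAP also disagrees with itself: Sections 2.2.3(a) and 2.4 name GI perforation for comparison, but the section that carries out the comparison defines a broader group and does not call for GI perforation separately.

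These events are rare and serious, and comparative tolerability of the two doses is a main reason for the trial. Protocol 1.4.3.2.1 reports GI fistulas (1%) and GI perforations (3%) separately for the 140 mg arm of XL184-301. A Perforations row that mixes in non-GI events cannot be read directly against the 3%.

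**Working it through.** The plan states no figure on this point, so the check compares definitions and then sets the scale.

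**Step 1. Where each type of event is counted**

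| Event | Protocol 9.4.1 | Endpoint lists (Protocol 2.1; SAP 2.2.3(a), 2.4) | SAP 8.3 |
|---|---|---|---|
| GI perforation | perforations | named | Perforations |
| Non-GI perforation | non-GI fistulas | not named | Perforations |
| GI fistula | fistulas | named | Fistulas |
| Non-GI fistula | non-GI fistulas | named | Fistulas |

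Only the second row differs between Protocol 9.4.1 and SAP 8.3.

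**Step 2. Direction of the difference, counting each subject once per group**

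- Perforations: the SAP group is GI plus non-GI perforation; the named comparison is GI perforation alone. The SAP count is equal or higher.
- Fistulas: the SAP group is GI plus non-GI fistula; the protocol's fistula groups combined also hold non-GI perforations. The SAP count is equal or lower.
- The second statement assumes that listing non-GI perforations under Perforations takes them out of Fistulas. SAP 8.3 does not say so. If they are meant to appear in both, the Fistulas count agrees with the protocol and the same event is counted in two groups.

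**Step 3. Size per reclassified subject**

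The change in an arm's rate is 1/N.

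- Planned size: N = 188/2 = 94, so 1/94 = 1.06%, about 1.1 percentage points.
- Maximum size: N = 250/2 = 125, so 1/125 = 0.8 percentage points.

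**Step 4. Scale against the historical rate (an assumption for the 140 mg arm only)**

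- Expected GI perforations at 3%: 0.03 × 94 = 2.8, about 3 subjects, or 3/94 = 3.2%.
- One added non-GI perforation would give 4/94 = 4.3%.

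That added event is hypothetical. Neither document gives a non-GI perforation rate, so the number of subjects who would move cannot be calculated and may be zero.

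There is no matching calculation for fistulas. The 1% in Protocol 1.4.3.2.1 is for GI fistulas only, whereas the group that gains or loses events is non-GI fistulas, for which no rate is given. Nor is 1% a safe base for all fistulas combined: the same section reports fistula as the cause of death in 3 cabozantinib subjects, and 3/214 = 1.4%.

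**The case against.** **Both groups depart from the safety endpoint.** A reader might infer this. The documents do not support it for fistulas: the endpoint lists name GI and non-GI fistulas in one phrase, and SAP 8.3(ii) covers the same events. The Fistulas line conflicts only with the rule in Protocol 9.4.1. Against the endpoint wording, only the Perforations line is broader.

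**GI perforation is an endpoint in its own right.** A reader might infer this too. It is one named component of a single additional endpoint, safety and tolerability.

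**The protocol leaves the detail to the SAP.** It does, and it also names both GI and non-GI perforations for separate summaries. But the grouping rule follows in the same paragraph and is specific. Reversing a stated rule is more than filling in detail, and SAP 4.8 asks for such changes to be documented.

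**SAP 8.3 is a list of topics, not a table shell.** This stands in part. Subrows are not excluded, so GI perforation might still be shown separately. The plan does not say that it will be.

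**Nothing is lost.** This largely stands. Table 4 tabulates all TEAEs by preferred term, Table 5 tabulates events to monitor by group and preferred term, and all AEs are listed. Either grouping can be rebuilt from the listings, though preferred-term rows cannot simply be added because a subject with two terms would count twice. The events to monitor are those under surveillance at database lock and are not listed in the SAP, so a separate GI perforation group there can be neither assumed nor ruled out.

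**No inference depends on it.** This stands. SAP 8 makes any safety comparison between arms exploratory, and no formal safety stopping rule uses these groups.

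**Conclusion.** The inconsistency is real and narrow. SAP 8.3 and Protocol 9.4.1 place non-GI perforations in different groups, and SAP 8.3 does not match the GI perforation comparison described in SAP 2.2.3(a) and 2.4. As written, the Perforations count can be higher than the GI perforation count, and the Fistulas count can be lower than under the protocol rule.

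The size is about 1.1 percentage points per reclassified subject at 94 per arm, or 0.8 at 125. The number of such subjects is unknown and may be zero. The fistula half of the statement also assumes that the SAP does not count non-GI perforations in both groups. The effect is confined to exploratory safety summaries; PFS, ORR and type I error are untouched. This is a low-priority correction, worth making because it is cheap and the rule as written is wrong against the SAP's own description of the comparison.

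**What to change.** Before unblinding, amend SAP 8.3 in one of two ways:

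- Show GI perforations as their own row, and count non-GI perforations with non-GI fistulas as Protocol 9.4.1 says.
- Keep the SAP grouping, document the departure from Protocol 9.4.1 and its reason under SAP 4.8, and still show a GI perforation row. In this case, also say whether a non-GI perforation is counted in one group or both.

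The pooled Perforations and Fistulas rows may stay as additions in either case. Fixing the preferred-term list for each group at the same time would remove the remaining ambiguity, but the correction does not depend on it.

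The cost is a few lines of SAP text and one or two more table rows with small counts. No data collection, sample size or efficacy analysis changes.

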8.4 Deaths

All reported subject deaths and whether death was causally associated with the disease under study (MTC) will be summarized by treatment arm for all subjects in the Safety population. The primary cause of death recorded on the CRF will be mapped to preferred term and system organ class using MedDRA. The coded terms will be merged with AE records to determine the relationship to study treatment.

Deaths will be summarized in 2 categories as follows:

- Deaths ≤ 30 days after the date of receipt of the last dose of study treatment
- Deaths > 30 days after the date of receipt of last dose of study treatment

Summary of primary cause of death will be tabulated under each category by causality to study disease and relationship to study drug.

All reported subject deaths will be listed.

8.5 Laboratory Assessments

8.5.1 Variables

The following treatment emergent laboratory abnormalities will be summarized. A treatment emergent laboratory abnormality is defined as one with an onset date on or after the date of the first dose of study treatment. Only abnormalities with a sample date through the end of the AE observation period will be tabulated.

Table 6: Laboratory Parameters to Be Summarized

Category	Abnormality	SDTM LBTESTCD	Grading System
-	WBC increased		
Hematology	WBC decreased	WBC	CTCAE
	ANC decreased	NEUT	CTCAE
	Basophils (continuous summary		
	only)	BASO	NA
	Lymphocytes increased		
	Lymphocytes decreased	LYM	CTCAE
	Monocytes (continuous summary		
	only)	MONO	NA
	Platelets decreased	PLAT	CTCAE
	Hemoglobin increased		
	Hemoglobin decreased	HGB	CTCAE
Serum chemistry	Albumin decreased	ALB	CTCAE
ž	ALP increased	ALP	CTCAE
	Amylase increased	AMYLASE	CTCAE
	ALT increased	ALT	CTCAE
	AST increased	AST	CTCAE
	Calcium increased		
	Calcium decreased	CA	CTCAE
	Creatinine increased	CREAT	CTCAE
	Creatinine clearance decreased	CREATCLR	CTCAE
	GGT increased	GGT	CTCAE
	Glucose increased	001	CTCTE
	Glucose decreased	GLUC	CTCAE
	LDH increased	LDH	Sponsor
	Lipase increased	LIPASE	CTCAE
	Magnesium increased	EIITISE	CICIE
	Magnesium decreased	MG	CTCAE
	Phosphate decrease	PHOS	CTCAE
	Potassium increased	THOS	CICIE
	Potassium decreased	K	CTCAE
	Sodium increased	T T	CICIE
	Sodium decreased	NA	CTCAE
	Total bilirubin increased	BILI	CTCAE
Urine chemistry	UPCR increased	PROTCRT	Sponsor
OTHIC CHCHHOU y	TSH increased	IROTORI	Бронзот
Endocrinology ¹	TSH decreased	TSH	HLN
Litaberinology	Free T4 increased	1511	111/11
	Free T4 decreased	T4FR	HLN
	Carcinoembryonic antigen	CEA	111211
Tumor Marker ²	Calcitonin	CLCTONN	
1 dillor ivial KCl	Calcioniii	CLCTONN	

 $^{^{1}}$ TSH is held in the SDTM "chemistry" laboratory category; will use HLN = high, low, normal classification based on normal range

Sponsor-defined grades are to be applied to the following analytes:

LDH

² Tumor markers carcinoembryonic antigen and calcitonin are efficacy laboratory parameters and will only be summarized for ITT population (Section 7.3).

- o Grade 1 if >ULN to \leq 2xULN
- o Grade 2 if >2xULN to ≤ 3xULN
- Grade 3 if >3xULN

UPCR

- o Grade 1 if ≥ 17.0 to ≤ 121.0 mg/mmol (≥ 0.15 to ≤ 1.0 mg/mg)
- o Grade 2 if > 121.0 to ≤ 396.0 mg/mmol (> 1.0 to ≤ 3.5 mg/mg)
- O Grade 3 if > 396.0 mg/mmol (> 3.5 mg/mg)

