- 7. The subject is  $\geq 18$  years old on the day of consent.
- 8. The subject has an ECOG (Eastern Cooperative Oncology Group) status  $\leq 1$  at screening.
- 9. The subject has adequate organ and marrow function, based upon the following laboratory criteria from assessments performed within 28 days before randomization
  - a. Absolute neutrophil count (ANC)  $\geq 1500/\text{mm}^3$
  - b. Platelets  $\geq 100,000/\text{mm}^3$
  - c. Hemoglobin  $\geq 9 \text{ g/dL}$
  - d. Total bilirubin  $\leq 1.5$  x the upper limit of normal (ULN). For subjects with known Gilbert's disease, total bilirubin  $\leq 3.0$  mg/dL.
  - e. Alanine aminotransferase (ALT) and aspartate aminotransferase (AST) < 3.0 x ULN
  - f. Serum creatinine ≤ 1.5 x ULN or creatinine clearance ≥ 50 mL/min (using the Cockcroft-Gault equation: CrCl (mL/min) = (140 age) x wt (kg) / (serum creatinine [mg/dL] x 72); for females multiply by 0.85
  - g. Urine protein/creatinine ratio (UPCR) ≤ 1 mg/mg (≤ 113.1 mg/mmol) or 24-hour urine protein < 1 g
  - h. Prothrombin time (PT)/INR or partial thromboplastin time (PTT) test results at screening  $\leq 1.3$  x the laboratory ULN
- 10. The subject is capable of understanding and complying with the protocol requirements and has signed the informed consent document.
- 11. Sexually active fertile subjects and their partners must agree to use medically accepted methods of contraception (defined in Appendix E) during the course of the study and for 4 months after the last dose of study treatment.
- 12. Female subjects of childbearing potential must not be pregnant at screening. Females of childbearing potential are defined as premenopausal females capable of becoming pregnant (ie, females who have had any evidence of menses in the past 12 months, with the exception of those who had prior hysterectomy). However, women who have been amenorrheic for 12 or more months are still considered to be of childbearing potential if the amenorrhea is possibly due to prior chemotherapy, antiestrogens, ovarian suppression or other reasons.

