#### 6.5.2.9 Proteinuria

Proteinuria is an anticipated AE with the inhibition of VEGF pathways and has been observed in cabozantinib clinical studies. Nephrotic syndrome has been reported with cabozantinib and other inhibitors of VEGF pathways.

During each safety assessment visit, proteinuria will be quantified by measuring the urine protein-to-creatinine (UPCR) ratio performed by the central lab. In addition, urine dipstick analysis performed by the local lab will be done at least every 8 weeks and as clinically indicated.

Management of proteinuria will be based on UPCR results provided by the central laboratory (see Table 6-10). However, since dipstick results from the local labs may be available prior to the UPCR results from the central laboratory, they can be used by the investigator for interim management. If the dipstick analysis shows proteinuria  $\geq 3+$ , the investigator may decide to

interrupt cabozantinib dosing until the UPCR result becomes and available and treatment decisions can be made.

Table 6-10: Guidelines for the Management of Treatment Emergent Proteinuria

Severity of Proteinuria (UPCR)	Action To Be Taken
≤ 1 mg/mg (≤ 113.1 mg/mmol)	No change in study treatment or monitoring
> 1 and < 2.0 mg/mg (> 113.1 and < 226.2 mg/mmol)	
 
No change in study treatment required
 
Consider confirming with a 24-hour protein excretion within 7 days
 
Repeat UPCR within 7 days and once every week as clinically indicated. If UPCR is < 1 mg/mg on two consecutive readings, then UPCR monitoring can revert to protocol-specific time points. (Second reading is a confirmatory reading and can be done within 1 week of the first reading.) If UPCR remains > 1 and < 2 for 1 month, check urine protein/creatinine per protocol or as clinically indicated.
 

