≥ 2.0 mg/mg (≥ 226.2 mg/mmol)	
 
Hold study treatment pending repeat UPCR within 7 days and/or 24-hour urine protein.
 
If ≥ 2.0 mg/mg on repeat UPCR or ≥ 2 g/24 hours on 24-hour urine collection, continue to hold study treatment and check UPCR every 7 days as clinically indicated. If UPCR decreases to < 2 mg/mg, restart study treatment at a reduced dose and monitoring of urine protein/creatinine should continue once every week as clinically indicated until the UPCR decreases to < 1 mg/mg or is determined to be stable (< 20% change) for 1 month at which point monitoring of UPCR can be per protocol or as clinically indicated.
 
If UPCR remains ≥ 2 and stable (< 20% change) for 1 month, can revert to monitoring per protocol or as clinically indicated. Continue to hold treatment until UPCR < 2.
 

Nephrotic syndrome	Discontinue all study treatment

UPCR, urine protein/creatinine ratio.

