8.5.2 Analysis

All laboratory data parameters and visits will include flags for values above or below laboratory reference ranges. Toxicity grades will be assigned programmatically by applying the CTCAE v5guidelines. Only results with assessment dates through the end of the safety observation period (see Section 4.5) will be tabulated in summary tables.

Laboratory summaries will be presented in SI units. Continuous laboratory test results will be summarized by treatment group using descriptive statistics for actual values and for changes from baseline by scheduled visit. Means and respective standard errors may also be presented at each scheduled visit (with visits shown on x-axis) for some laboratory parameters. For continuous laboratory test results which are below or above the quantification level, the imputed values as described in Appendix C will be used for deriving the grade and then summarized.

Tables summarizing the incidence of laboratory abnormalities by maximum post-baseline CTCAE grade overall and by baseline grade will be presented. Frequencies of laboratory abnormalities of worsening $\geq +1$ and +2 change from baseline to worst grade value after first dose will also be summarized.

In addition, the following summaries will also be presented:

- A. Liver function abnormalities will be assessed as follows:
 - Shift from baseline based on normal ranges
 - Subject-incidence of treatment-emergent liver function test abnormalities according to baseline criteria
 - >3xULN (ALT or AST), <2xULN ALP, and >2xULN Total Bilirubin
 - >3xULN (ALT or AST), >=2xULN ALP, and >2xULN Total Bilirubin

- B. For renal failure surveillance, a summary of subjects meeting renal failure laboratory screening criteria as shown below will be provided:
 - Serum creatinine >= 3.0xULN and >= 2.0x baseline value or
 - Estimated glomerular filtration rate (eGFR) \leq 50% of the baseline value or
 - eGFR < 30 mL/min/1.73 m² and ≥ 25% reduction from the baseline value eGFR = 186 x (Creatinine in mmol per L / 88.4)-1.154 x (Age)-0.203 x (0.742 if female) x (1.210 if black) [MDRD186 formula on the National Kidney Foundation FAQ, #10: https://www.kidney.org/sites/default/files/docs/12-10-4004 abe faqs aboutgfrrev1b singleb.pdf]

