- C. Categorical summaries for baseline status for TSH and Free T4 will be presented. In addition categorical summaries for post-baseline TSH and Free T4 status among subjects with TSH and Free T4 in the normal range at baseline will also be presented.

For descriptive summaries for change from baseline analyses, only central lab results will be considered. For analyses of shift in grade from baseline or worst grade after baseline, all available results will be considered regardless of whether from the central or local lab.

Table 7: Laboratory Summaries

	Include Central Lab	Include Local Lab
Summary Type	results?	results?
Subject Incidence of Treatment Emergent Laboratory		
Abnormalities in Selected Laboratory Tests by CTCAE Grade	Y	Y
Change from Baseline in Laboratory Values	Y	N
Shift from Baseline in Laboratory Values by CTCAE Grade	Y	Y
Shift from Baseline of at Least 2 Grades by CTCAE Grade	Y	Y
Shift from Baseline in Laboratory Values by High/Low/Normal	Y	Y
Shift from Baseline in Laboratory Values by Sponsor-defined		
Grades	Y	Y
Subject Incidence of Laboratory Abnormalities with a Between-		
Arm Difference of ≥5% (All Grades) or ≥2% (Grades 3-4)	Y	Y
Subject Incidence of Treatment-Emergent Liver Function Test		
Abnormalities According to Baseline Criteria	Y	Y
Subject Incidence of Treatment-Emergent Renal Function Test		
Abnormalities According to Baseline Criteria	Y	Y

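### The SAP's UPCR Grade 1/2 limit is printed as 121.0 mg/mmol = 1.0 mg/mg, but 1.0 mg/mg is 113.1 mg/mmol by the documents' own conversion, so the two halves of the rule disagree

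*SAP*

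**What the plan says.** SAP 8.5.1 lists UPCR in Table 6 as an analyte graded by the sponsor's own scale; LDH is the only other one. Each UPCR limit appears in mg/mmol with a mg/mg equivalent in parentheses:

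- Grade 1: "Grade 1 if ≥ 17.0 to ≤ 121.0 mg/mmol (≥ 0.15 to ≤ 1.0 mg/mg"
- Grade 2: "Grade 2 if > 121.0 to ≤ 396.0 mg/mmol (> 1.0 to ≤ 3.5 mg/mg"
- Grade 3: "if > 396.0 mg/mmol (> 3.5 mg/mg"

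The protocol gives the same ratio in both units at two places. Inclusion criterion 9g has "Urine protein/creatinine ratio (UPCR) ≤ 1 mg/mg (≤ 113.1 mg/mmol". Table 6-10 (section 6.5.2.9) has "≤ 1 mg/mg (≤ 113.1 mg/mmol" for its lowest category and "≥ 2.0 mg/mg (≥ 226.2 mg/mmol" for a higher one.

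The grades are used in SAP 8.5.2. Table 7 plans a summary titled "Shift from Baseline in Laboratory Values by Sponsor-defined" grades, which takes both central and local results. The text of 8.5.2 adds that worsening by grade, as "change from baseline to worst grade value after first dose will also be summarized". The same section says that laboratory summaries are reported in SI units.

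**The concern.** The two units describe one ratio, so a single conversion factor must link every pair of printed limits. The pair 121.0 mg/mmol and 1.0 mg/mg does not fit the factor that links all the others. Because the figure stands in both the Grade 1 and the Grade 2 line, it sets the cut-off between those grades.

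Two programmers could each follow the SAP and produce different UPCR tables, one coding mg/mmol and the other mg/mg.

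The boundary also matters elsewhere in the trial. A UPCR of 1 mg/mg is the eligibility limit, the level above which Table 5-1 asks for a confirmatory test, and the first boundary in Table 6-10. A shift from Grade 1 to Grade 2 is meant to show that a subject has crossed it. If mg/mmol is programmed, a subject can exceed 1 mg/mg by the protocol's definition and still be tabulated in the grade whose printed ceiling is 1.0 mg/mg. Laboratory changes are among the listed endpoints for comparing the two doses.

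**Working it through.** **Inputs.** The protocol's factor is 113.1 mg/mmol per mg/mg, from criterion 9g and Table 6-10 (113.1/1 = 113.1; 226.2/2.0 = 113.1). The three UPCR limits come from SAP 8.5.1.

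**Step 1: try to reproduce each printed limit.** Formula: mg/mmol = mg/mg × 113.1.

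| Source | mg/mg | Printed mg/mmol | Implied factor | mg/mg × 113.1 | Departure |
|---|---|---|---|---|---|
| SAP, Grade 1 lower limit | 0.15 | 17.0 | 17.0/0.15 = 113.3 | 16.97 | +0.2% |
| SAP, Grade 1/2 limit | 1.0 | 121.0 | 121.0/1.0 = 121.0 | 113.1 | +7.0% |
| Protocol Table 6-10 | 2.0 | 226.2 | 226.2/2.0 = 113.1 | 226.2 | 0% |
| SAP, Grade 2/3 limit | 3.5 | 396.0 | 396.0/3.5 = 113.1 | 395.85 | +0.04% |

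The SAP's outer limits reproduce to within rounding. The middle one does not.

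**Step 2: convert the odd figure back.** 121.0/113.1 = 1.07 mg/mg, against the printed 1.0.

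**Step 3: find the results on which the two halves disagree.** The mg/mmol half puts the cut at 121.0, and the mg/mg half puts it at 1.0 × 113.1 = 113.1. They disagree for results above 113.1 and up to 121.0 mg/mmol, a band of 121.0 − 113.1 = 7.9 mg/mmol. For example, 118 mg/mmol is 118/113.1 = 1.04 mg/mg: Grade 1 by the first half, Grade 2 by the second.

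**Step 4: set the band against the grade ranges.**

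- Share of the Grade 2 range: 7.9/(396.0 − 113.1) = 7.9/282.9 = 2.8%.
- Widening of the Grade 1 range: 7.9/(113.1 − 17.0) = 7.9/96.1 = 8.2%.

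These are shares of range width, not of subjects.

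**Step 5: a second check on the factor.** The eGFR formula in SAP 8.5.2 divides creatinine by 88.4. Read as micromol/L per mg/dL, that constant gives 1000/8.84 = 113.1 mg/mmol per mg/mg, the same factor. The finding does not depend on this check.

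**Step 6: other explanations.** Rounding moves the other two SAP limits by at most 0.2%, so it does not account for 7.0%. A misread digit in the PDF is unlikely, because 121.0 stands identically in two lines. One ratio cannot have a different factor at its middle cut-off only.

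**The case against.** The arithmetic is not in dispute. The case for treating this as trivial has four parts.

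- **mg/mmol is probably the operative half.** It is printed first, and laboratory summaries are in SI units. On that scale the grades have no gap or overlap, and they would be applied alike to both arms. This is a fair reading, but it is not a stated grading rule. It also makes the faulty figure the one most likely to be programmed, so it does not remove the defect.
- **The grades are the sponsor's own.** No outside standard in the documents fixes the cut, so 121.0 could be deliberate and the parenthesis wrong. This cannot be excluded outright. However, the mg/mg limits are 0.15, 1.0 and 3.5, the other two convert correctly, and the protocol already uses 1 mg/mg = 113.1 mg/mmol. All of this points to 113.1 as the intended figure.
- **The reach is small.** Only one row of Table 7 names sponsor-defined grades. The incidence, shift and two-grade rows are labelled as CTCAE. The between-arm row uses all grades or Grades 3-4, and moving the Grade 1/2 cut changes neither. Applying the worsening-by-grade text to UPCR is an inference. Between-arm safety comparisons are exploratory (SAP section 8). All of this stands, and it limits the size of the point.
- **No practical effect is shown.** This also stands: the range-width percentages say nothing about how many results fall in the band.

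**Conclusion.** The concern holds. The Grade 1/2 cut-off for UPCR in SAP 8.5.1 contradicts itself: 121.0 mg/mmol and 1.0 mg/mg differ by 7% on the factor that fits every other printed UPCR limit in both documents. Results in a 7.9 mg/mmol band can be graded either way.

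The consequence is modest. It touches Grade 1 versus Grade 2 counts and shifts in descriptive tables. Eligibility and management use the protocol's own consistent limits and do not depend on the SAP grade; Grade 3 counts, PFS and ORR are likewise untouched.

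The contradiction rests only on the protocol's conversion factor. That 113.1 is the right replacement rests also on the mg/mg limits being the intended ones, which the pattern of figures supports strongly without proving it. The correction is worth making because the error sits in a rule that has to be programmed and costs almost nothing to remove.

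**What to change.** In SAP 8.5.1, replace 121.0 with 113.1 mg/mmol in both the Grade 1 and the Grade 2 line and leave the mg/mg limits as they are. The cut-offs then read 17.0, 113.1 and 396.0 mg/mmol, all on one factor. If 121.0 was deliberate, the SAP should say so, print 1.07 mg/mg beside it, and explain the departure from the protocol's boundary. In either case, state which unit drives the grading.

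The cost is one number in two lines and the matching line of the grading program. SAP 4.8 allows minor corrections through an addendum approved before unblinding.

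Two queries for the authors while the section is open; neither is claimed as an error, and the finding does not rest on them:

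- Confirm that creatinine enters the eGFR formula in SAP 8.5.2 in micromol/L. The divisor 88.4 fits only that unit, and the printed millimole may come from PDF conversion.
- Confirm that CTCAE version 5 is intended for programmatic laboratory grading in SAP 8.5.2. If so, cite it, since the reference list has only version 4.0.
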